7.7. Study Drug Overdose Management

The medical monitor must be contacted in the event of any study drug overdose.

An overdose is defined as a known deliberate or accidental administration of study drug, to or by a study patient, at a dose above that assigned to that individual patient according to the study protocol.

For this study, any dose of relugolix > 240 mg within a 24-hour window is an overdose, except for the 360-mg loading dose. The sponsor does not recommend specific treatment for an overdose; supportive treatment should be provided as clinically applicable.

In the event of an overdose, the investigator or treating physician should:

- Contact the medical monitor immediately;
- Closely monitor the patient for adverse events and laboratory abnormalities;
- All overdose events are to be reported within 24 hours of awareness by the study site, using a serious adverse event form, whether or not the overdose is associated with an adverse event;
- If possible, obtain a plasma sample for PK analysis within 2 days from the date of the last dose of study drug if requested by the medical monitor (determined on a case-by-case basis); and

- Document the quantity of the excess dose as well as the duration of the overdosing in the eCRF.

The medical monitor, in consultation with the investigator, will make decisions regarding patient status and potential dose interruptions, based on the clinical evaluation of the patient.

7.8. Pregnancy Reporting

If the partner of any patient becomes pregnant during the study or through 4 months after the last dose of study drug, the investigator must inform the sponsor of the pregnancy.

The patient should remain on study drug treatment, unless otherwise indicated.

If the patient agrees, the patient's pregnant partner should be notified and requested to sign a Release of Information form, permitting transfer of information regarding the pregnancy and outcome to the sponsor.

A pregnancy is to be reported to the sponsor within 24 hours of awareness by the study site personnel, using the partner pregnancy report forms. The expected date of delivery or expected date of the end of the pregnancy, last menstruation, estimated conception date, pregnancy result, and neonatal data, etc, should be included in this information, as available.

The investigator will follow the medical status of the mother, as well as the fetus, and will report the outcome to the sponsor.

7.9. Benefit/Risk Assessment

Summaries of findings from both nonclinical and clinical studies conducted with relugolix can be found in the current version of the Investigator Brochure.

The risk assessment and mitigation strategies for this protocol are outlined in [Table 7-3](#).

Table 7-3 Relugolix Potential Risks and Mitigation

Potential Risk of Clinical Significance	Mitigation Strategy	
	Impact on Eligibility	Monitoring and Stopping Criteria
Hepatic Enzyme Increases Isolated increases in hepatic enzymes have been observed in prior clinical studies. Hepatic enzyme increases, considered an important potential risk of treatment with relugolix, are closely monitored in accordance with FDA guidelines for assessing drug-induced liver injury [FDA, 2009] in all relugolix studies.	Exclusion criteria for AST and ALT > ULN; total bilirubin values > ULN unless consistent with Gilbert's syndrome.	Liver chemistry will be monitored during the study. Appropriate liver stopping criteria and follow-up procedures are detailed in Section 7.5.2 .
Phospholipidosis Data from nonclinical studies in rats and monkeys showed histopathological changes consistent with PLD. PLD by itself is not adverse. No clinical	Patients with significant underlying medical conditions are excluded.	Routine safety monitoring including laboratory assessments, ECGs, and assessment of adverse events; visual

Potential Risk of Clinical Significance	Mitigation Strategy	
	Impact on Eligibility	Monitoring and Stopping Criteria
evidence of relugolix-related PLD-associated toxicity has been observed nor was there a clinically meaningful increase in a biomarker of PLD assessed in phase 2 clinical studies.		acuity will be evaluated during the study.
Risks Associated with Medical Castration Acute and subsequent chronic symptoms of medical castration (reduction of testosterone to ≤ 50 ng/dL [1.7 nmol/L]) include vasomotor symptoms or hot flushes, disturbed sleep related to vasomotor symptoms, decreased libido, and fatigue or loss of energy. These side effects are usually not severe and can be managed with anticipatory guidance. Long-term suppression of testosterone is associated with well-characterized risks including bone loss, decreased muscle mass, possible changes in insulin sensitivity with increased risk of diabetes, altered lipid metabolism, and possible increased risk of cardiovascular disease [Oefelein, 2002; Lopez, 2005; Diamond, 1998; Keating, 2006; Braga-Basaria, 2006; Saigal, 2007; Tsai, 2007; D'Amico, 2007; Efstathiou, 2009].	-	Effects can usually be managed with appropriate anticipatory guidance (eg, diet and exercise programs) or supportive therapy when required (eg, lipid-lowering or bone-sparing agents).
Metabolic Changes Metabolic changes (insulin resistance, dyslipidemia, and increased weight) with increased risk of diabetes are a potential risk of the hypoestrogenic state induced by relugolix.	-	Fasting lipids and glucose will be monitored during the study.
Loss of Bone Mineral Density Loss of bone mineral density is considered a potential risk of treatment with relugolix in the prostate cancer indication.	-	Fractures will be assessed through adverse event monitoring. Use of anti-resorptive bone therapy, such as bisphosphonates or denosumab, may be considered by the treating physician.

Abbreviations: ALT; alanine aminotransferase; AST, aspartate aminotransferase; ECG, electrocardiogram; FDA, Food and Drug Administration; PLD, phospholipidoses; ULN, upper limit of normal

8. DATA QUALITY ASSURANCE

8.1. Clinical Procedures

Sponsor personnel or designee(s) will visit the study site if necessary prior to initiation of the study to review information about the study drug, protocol requirements, eCRFs, monitoring requirements, reporting of serious adverse events, and to ensure a full understanding of the investigator site file with the site personnel.

8.2. Monitoring

This study will be monitored by the sponsor (or designee) in accordance with current Good Clinical Practice regulations. By signing this protocol, the investigator grants permission to Myovant Sciences GmbH (or designee) and appropriate regulatory authorities to conduct on-site monitoring of all appropriate study documentation. In order to assure the accuracy of data collected in the eCRF, it is mandatory that representatives of the sponsor (or designee) have access to original source documents (eg, patient records, patient charts, and laboratory reports). During the review of these documents, the anonymity of the patient will be respected with strict adherence to professional standards of confidentiality. A study monitor will contact and visit the site regularly and will be allowed, on request at a mutually acceptable time, to inspect the various records of the study. It will be the study monitor's responsibility to inspect the eCRF at regular intervals throughout the study, to verify the adherence to the protocol and the completeness, correctness and accuracy of all eCRF entries, and to meet with the investigator to discuss study progress and compliance with the protocol and Good Clinical Practices. The study monitor should have access to laboratory test results and any other source records and data needed to verify the entries on the eCRF. The investigator agrees to cooperate with the study monitor to ensure that any problems detected in the course of these monitoring visits are resolved. For this study, patient data will be entered into a sponsor-approved electronic database and combined with data provided from other sources in validated datasets then transmitted electronically to the sponsor (or designee).

Management of clinical data will be performed in accordance with applicable sponsor-approved standards and data cleaning procedures to ensure the integrity of the data (eg, removing errors and inconsistencies in the data).

Adverse events and concomitant medications terms will be coded using the Medical Dictionary for Regulatory Activities (MedDRA) and the World Health Organization Drug Dictionary Enhanced, respectively.

The investigator will retain original source documents and the sponsor will receive eCRF-required data as electronic datasets. Patient initials will not be collected or transmitted to the sponsor.

8.3. Independent Data and Safety Monitoring Board

An independent Data and Safety Monitoring Board will review available safety data, as appropriate, on a periodic basis throughout the conduct of the study. Details of the Data and Safety Monitoring Board will be captured in a charter prior to the start of the study.

8.4. Steering Committee

A Steering Committee consisting of experts in the field of prostate cancer and staff members of Myovant Sciences GmbH will be established to provide oversight for the clinical trial, study design, study conduct, data analysis, and presentation and publication of the study data. Details of the Steering Committee responsibilities will be captured in a separate charter.

9. STATISTICAL CONSIDERATIONS AND DATA ANALYSES

A statistical analysis plan will describe the detailed statistical methods and analyses for this study. The statistical analysis plan will be prepared and finalized prior to database lock and analysis of the primary and secondary endpoints.

All confidence intervals will be 2-sided at an alpha level of 0.05 unless otherwise specified. The methodology to be used to maintain a study-wide type I error rate of 0.05 across primary and secondary endpoint testing will be described in the statistical analysis plan.

All efficacy and safety measures over the course of the study will be presented. Continuous data will be summarized by means, standard deviations, medians, maximum, minimum, and number of patients. Categorical data will be summarized by counts and percentages.

9.1. Randomization Methods

Central randomization will be used and treatment allocation will be 2:1, relugolix to leuprolide acetate 3-M depot. Randomization will be stratified by the following factors:

- Geographic Region: North and South America versus Europe versus Asia and Rest of World;
- Presence of Metastatic Disease: yes versus no;
- Baseline Age: ≤ 75 years old versus > 75 years old.

Stratified efficacy analyses will incorporate these 3 stratification factors unless otherwise specified.

9.2. Analysis Populations

The Intent-To-Treat (ITT) population will consist of all patients randomized to treatment who have taken at least one dose of study treatment. This will be the primary population used for the efficacy analysis. Patients will be analyzed according to their randomized treatment assignment.

The Per-Protocol population will consist of those members of the ITT population who have no major protocol deviations as defined in the statistical analysis plan, considering the following protocol deviations but not limited to:

- Those who entered the study even though they did not satisfy the entry criteria;
- Those who developed withdrawal criteria during the study but were not withdrawn;
- Those who received the wrong treatment or incorrect dose;
- Those who received an excluded concomitant treatment.

The Per-Protocol population will not be analyzed if this population comprises more than 95% or less than 50% of the ITT population. The Per-Protocol population will be used as a sensitivity analysis of the ITT population for the primary efficacy endpoint and secondary endpoints. The Per-Protocol population will be identified prior to the database lock.

The primary population for safety analyses will be the Safety population, defined as all patients who receive at least one dose of any study treatment. Patients will be analyzed according to the treatment actually received, regardless of their randomized treatment assignment.

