- Evaluation Criterion 2: to establish the non-inferiority of relugolix compared to leuprolide acetate 3-M depot as assessed by the cumulative probability of sustained testosterone suppression to castrate levels. The lower bound of the 95% confidence interval for the difference in the cumulative probability of sustained testosterone suppression to castrate levels between the 2 treatment groups will be calculated and must be greater than or equal to the non-inferiority margin of -10% to meet this criterion.

The 2-sided type I error rate will be 0.05 for each individual evaluation criterion.

Secondary Efficacy Endpoints:

1. Castration rate: the cumulative probability of testosterone suppression to ≤ 50 ng/dL (1.7 nmol/L) prior to dosing on Week 1 Day 4, and prior to dosing on Week 3 Day 1;
2. Profound castration rate: the cumulative probability of testosterone suppression to ≤ 20 ng/dL (0.7 nmol/L) from Week 25 through Week 49;
3. PSA response rate: proportion of patients with a $\geq 50\%$ decrease in PSA from baseline at Week 3 and confirmed at Week 5;
4. Undetectable PSA rate: proportion of patients with PSA concentration < 0.2 ng/mL (0.2 μ g/L) at the Week 25 visit;
5. Time to testosterone recovery in approximately 100 relugolix-treated and approximately 50 leuprolide acetate-treated patients who complete 48 weeks of treatment and do not start alternative androgen deprivation therapy within 12 weeks after the last dose of relugolix or within 24 weeks following the last received injection of leuprolide acetate. Kaplan-Meier methods will be used to describe survival distributions;
6. Quality of Life: absolute values and changes from baseline in the scores of the EORTC-QLQ-C30 global health domain, and the EORTC-QLQ-PR25 sexual activity and hormonal-

treatment-related symptom subdomains, at regular intervals during treatment, and as applicable at the Follow-up and/or End-of-Study visits will be presented. Additionally, absolute values and changes from baseline of the remaining domains in the EORTC QLQ-C30 and EORTC QLQ-PR25, as well as EQ-5D-5L, at regular intervals during treatment, and as applicable during the Follow-up visits will be presented. Change from baseline will be analyzed using mixed-model repeated measures methodology;

7. Time to PSA progression;
8. Proportion of patients with confirmed PSA progression among those who have achieved sustained testosterone suppression during the 48-week treatment period.

Exploratory Endpoints:

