Patient not meeting criteria for testosterone suppression to castrate level	Patients with disease progression while on study drug, assuming adequate testosterone suppression (testosterone level ≤ 50 ng/dL [1.7 nmol/L]), may receive radiotherapy as prescribed by the investigator. In the setting of rising PSA patients may also receive enzalutamide. For patients requiring other systemic antineoplastic therapy during the treatment period, the investigator should contact the medical monitor.
Laboratory abnormality defined by protocol: ALT or AST $> 8 \times$ ULN; or ALT or AST $> 5 \times$ ULN and persists for more than 2 weeks; or ALT or AST $> 3 \times$ ULN in conjunction with elevated total bilirubin $> 2 \times$ ULN or INR > 1.5 ; or ALT or AST $> 3 \times$ ULN with appearance of fatigue, nausea, vomiting, right upper quadrant pain or tenderness, fever, rash and/or eosinophilia ($> 5\%$)	If any of these liver test abnormalities develop, study drug should be discontinued immediately with appropriate clinical follow-up (including repeat laboratory tests, until a patient's laboratory profile has returned to normal/baseline status).
Confirmed QTc prolongation of more than 500 msec, in the absence of a pacemaker, as read by a cardiologist	If QTc prolongation of > 500 msec in the absence of a pacemaker occurs, the ECG must be repeated. Confirmed QTc prolongation, measured by Fridericia's formula [QTcF = QT/(RR $^{0.33}$)], will result in removal of the patient from treatment.
Patients who have a clinically significant decrease in visual acuity as evaluated by an ophthalmologist that may be related to study drug treatment	
Gross noncompliance with protocol	Patients who are, in the opinion of the investigator or the medical monitor, non-compliant with the protocol's requirements
Patient decision	Patients may permanently discontinue study treatment at any time for any reason. Following study drug discontinuation, patients should attend the protocol-required safety follow-up visit.
Sponsor discontinuation of study	The sponsor reserves the right to terminate the study anytime as described in Section 10.3.3. The sponsor will terminate this study following completion of study objectives, or earlier if deemed necessary.

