9.9. Sample Size

To calculate the sample size required for the primary efficacy endpoint of this study, the following assumptions have been made:

- True probabilities of sustained testosterone suppression are 94% and 96% for relugolix and leuprolide acetate, respectively;
- 2:1 randomization ratio (relugolix:leuprolide acetate); and
- Dropout rate of 15%.

The assumed probability of sustained testosterone suppression for relugolix arm is 94%. It was estimated based on the predicted dose-response relationship for the effect of relugolix on testosterone suppression in patients with prostate cancer (data from phase 2 studies C27002 and C27003). The assumed castration rate of 96% for leuprolide acetate was based on the results from degarelix phase 3 registration program [[Shore, 2013](#)].

For Evaluation Criterion 1, 610 patients in the relugolix group will provide approximately 90% power to rule out a fixed probability of sustained testosterone suppression of < 90% at a 2-sided type I error rate of 0.05.

For Evaluation Criterion 2, with the non-inferiority margin of -10% and an overall 2-sided type I error rate of 0.05, a total of approximately 915 patients (610 relugolix, 305 leuprolide acetate) will yield at least 99% power in declaring the non-inferiority of relugolix compared to leuprolide acetate.

The final analysis will be performed separately for individual evaluation criterion using data collected through 48 weeks after enrollment of approximately 915 patients.

Approximately 915 patients will be randomized in order to fulfill the regulatory requirements of all participating countries.

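### As worded, the per-protocol set can drop men who fail the primary endpoint but stay on drug, which would bias that sensitivity analysis toward non-inferiority; the ITT result is unaffected

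*Protocol*

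**What the plan says.** Section 9.2 builds the per-protocol set from ITT members without major deviations. The final list is left to the SAP, but the protocol names four kinds of deviation to consider. One is "Those who developed withdrawal criteria during the study but were not withdrawn". The set serves as a sensitivity analysis for the primary and secondary endpoints and is to be fixed before database lock. The same section adds a size rule: "The Per-Protocol population will not be analyzed if this population comprises more than 95% or less than 50% of the ITT population".

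Section 4.7 says that the events in Table 4-1 lead to removal from therapy, either for good or until the cause is found and resolved. One row is headed "Patient not meeting criteria for testosterone suppression to castrate level". The comment beside that row deals with a different group: men whose disease progresses although testosterone is adequately suppressed, and the treatments they may receive.

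Section 9.3.1 makes a testosterone value above 50 ng/dL on treatment from Week 5 the event that ends sustained castration. Evaluation Criterion 2 requires the lower 95% bound for relugolix minus leuprolide to be at least -10%. Section 9.2 makes ITT (randomized and dosed) the primary efficacy population.

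**The concern.** Put together, the Table 4-1 heading and the 9.2 item let the primary event itself decide who is in the per-protocol set. Two men with the same testosterone failure are treated differently. The one who is withdrawn counts as a failure, and the one who continues can disappear. Removing failures raises both arms' rates, and the arm with more failures gains more, so a true deficit of relugolix shrinks toward zero.

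The choice to continue or withdraw is not random. The study is open-label (Section 5.8), values above 50 ng/dL are reported to the investigator (Section 6.6.1.1), one withdrawal criterion, the dose hold beyond 10 days, applies to relugolix only (Table 4-1), and a depot cannot be stopped once given (Section 5.6). Fixing the set before database lock therefore does not make the selection blind to outcome.

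At stake is whether the per-protocol analysis could contradict a doubtful non-inferiority result. The size rule adds to this, since it lets the analysis go unreported at either extreme.

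**Working it through.** **Inputs.** From Section 9.9: "True probabilities of sustained testosterone suppression are 94% and 96% for relugolix and leuprolide acetate, respectively"; 610 relugolix and 305 leuprolide patients; 15% dropout. From the synopsis: "The 2-sided type I error rate will be 0.05 for each individual evaluation criterion". Margin -10%. Assumed, because the documents do not give it: f, the share of failing men who stay on drug and are excluded, from 0 to 1. Simple proportions are used, without Kaplan-Meier censoring.

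**The plan's own figures.** The protocol says "610 patients in the relugolix group will provide approximately 90% power". After dropout n = 610 × 0.85 = 518. Power = Φ{[0.04 − 1.96·√(0.90×0.10/518)] / √(0.94×0.06/518)} = Φ(1.36) = 91.3%; exact binomial gives 91.2%. For Criterion 2 with 518:259, SE = √(0.94×0.06/518 + 0.96×0.04/259) = 0.0160 and power = Φ(0.08/0.0160 − 1.96) = 99.9%. Both stated powers reproduce.

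**Effect of removing failures.** For true rate p and arm size n, the per-protocol rate is p·n / [n − f(1−p)n]. The chance of declaring non-inferiority is Φ[(d + 0.10)/SE − 1.96], with d the per-protocol difference and SE its unpooled standard error. Same f in both arms:

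| True rates | f | Per-protocol rates | Difference (points) | P(declare NI) | Set as share of ITT |
|---|---|---|---|---|---|
| 86/96% | 0 | 86.0/96.0% | -10.0 | 2.5% | 100% |
| 86/96% | 0.25 | 89.1/97.0% | -7.85 | 26% | 97.3% |
| 86/96% | 0.5 | 92.5/98.0% | -5.49 | 91% | 94.7% |
| 86/96% | 0.75 | 96.1/99.0% | -2.88 | about 100% | 92.0% |
| 88/96% | 0 | 88.0/96.0% | -8.0 | 21% | 100% |
| 88/96% | 0.5 | 93.6/98.0% | -4.34 | 99% | 95.3% |
| 94/96% | 0 | 94.0/96.0% | -2.0 | about 100% | 100% |
| 94/96% | 0.5 | 96.9/98.0% | -1.05 | about 100% | 97.3% |
| 94/96% | 1 | 100/100% | 0 | about 100% | 94.7% |

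Worked row, 86/96% at f = 0.5: failures are 85.4 and 12.2, of which 42.7 and 6.1 are removed. Rates are 524.6/567.3 = 92.47% and 292.8/298.9 = 97.96%. d = -5.49 points, SE = 0.0138, and Φ(0.0451/0.0138 − 1.96) = Φ(1.3) = 0.91. The set is 866.2/915 = 94.7%.

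**Interplay with the size rule.** 5% of 915 is 45.75, so the set stays above 95% with up to 45 exclusions. If these failures are the only exclusions, the analysis is run once f reaches 45.75/97.6 = 0.47 at 86/96%, but only at 45.75/48.8 = 0.94 at 94/96%. Below that it is run only if other deviations add enough exclusions. For example, 86/96% at f = 0.25 removes 24.4 men, and about 22 more would be needed.

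**Can skipping above 95% hide a contradiction?** Take the most adverse 45 exclusions (33 relugolix successes, 12 leuprolide failures). At 573/610 vs 293/305 the ITT lower bound is -5.0% and the worst per-protocol bound is -8.4%, still inside the margin. At 549/610 vs 293/305 the ITT bound is -9.3%, a pass, while the worst per-protocol bound is -13.1%.

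**The case against.** A reader might infer that the plan deletes every man who fails the primary endpoint, that the size rule cancels the analysis, and that the non-inferiority claim is therefore unsound. The documents do not support that, for these reasons:

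- The items in 9.2 are deviations to consider, and the operative list belongs to the SAP.
- The Table 4-1 row gives no removal instruction for testosterone above 50 ng/dL, and its comment concerns men who are suppressed. Section 6.6.1.1 speaks only of reporting and possible reanalysis of such values. A single high value is thus not clearly a withdrawal criterion that was ignored.
- Failing men who are withdrawn stay in the set as events.
- Neither evaluation criterion is decided on the per-protocol set; ITT keeps every failing man.
- The size rule bites only above 95% or below 50% of the whole ITT set. At the planning rates, skipping above 95% cannot overturn non-inferiority.
- Inflated rates at 94/96%, such as 96.9% for relugolix at f = 0.5, would not be reported if these were the only exclusions, because the set would be 97.3% of ITT. There the rule suppresses a flattering result.

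All of this stands and limits the point. It does not remove it. The protocol itself names the category, itself puts the testosterone heading among the reasons for removal, and itself fixes the size rule. Nothing in 9.2 prevents the outcome-dependent reading.

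**Conclusion.** The point holds as a weakness of the per-protocol sensitivity analysis for Evaluation Criterion 2, under the literal reading of the Table 4-1 heading. The direction is toward non-inferiority. The size depends on f, which is unknown: there is no bias at f = 0, and on the margin the false-declaration rate of the check goes from 2.5% to about 26% at f = 0.25 and about 91% at f = 0.5. The f = 0.25 figure would be seen only if other deviations brought the set to 95% of ITT or below. At the planning rates the conclusion would not change. The weakness matters when failures are more common than planned or other exclusions accumulate, which is when an independent check is wanted. The size rule is a lesser issue: it could hide a contradictory result only when the ITT bound is close to -10%, or when the set falls below half of ITT. These figures rest on simple proportions, 610:305 and equal f in both arms. The primary analysis needs no change.

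**What to change.** In Section 9.2, state that a post-baseline testosterone value above 50 ng/dL is never by itself a ground for per-protocol exclusion, that it counts as an event whether or not the man is withdrawn, and that all other deviations are judged without reference to testosterone results. The SAP's deviation list should follow this.

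Report the per-protocol analysis for Evaluation Criterion 2 whatever its share of ITT.

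The sponsor should reconcile the heading of the testosterone row in Table 4-1 with its comment. Which clinical rule is right is not for this review to say.

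Cost: a few sentences in 9.2, one table row clarified and one extra results table. Sample size and primary analysis are untouched.
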